Participants will be provided with the Daily Symptom Diary on their second visit, prior to treatment initiation. It will be a notebook with the above questions printed on each page with a total of 30 entries and 5 extra pages in the back for any other information that the participant may wish to include (Attachment 3). The completeness of entries and pattern of symptoms will be assessed on the subsequent visits on Day 14 and Day 29. All information will then be noted and uploaded to the study database subsequently. Participants will need to have at least 80% completed entries i.e. 22 diary entries throughout the study period. Any missing entry will be considered as no bowel movements for that day. Any subject with insufficient data entry of less than 22 entries will be categorized a non-responder. No patient identifiers will be included in the diary, other than subject number that corresponds to the master study

enrollment log, which will be maintained electronically. Patients will be given sequential study ID numbers (1 up to 100) upon enrollment into the study.

PHASE 3: POST-TREATMENT FOLLOW-UP

A post-treatment follow-up visit would be scheduled with the PI on Day 29 or the first business day after completion of the crofelemer course. The following variables will be obtained and analyzed for the study -

1. Age (in years)
2. Gender (Male/Female/Other)
3. Ethnicity (Caucasian/Hispanic/African American/Native American/Asian/Other)
4. BMI (in kg/m²)
5. Number of weeks/years of diarrhea fulfilling entry criteria
6. Number of stools per day (Day 0)
7. Number of stools per day (Day 14)
8. Number of stools per day (Day 28)
9. Total number of stools per week (Week 1, 2, 3, and 4)
10. Average consistency of stools (Day 0)
11. Average consistency of stools (Day 14)
12. Average consistency of stools (Day 28)
13. Previous use of other anti-diarrheal agents (Yes/No)
14. Average number of anti-diarrheal agents used per week (Day 0)
15. Average number of anti-diarrheal agents used per week (Day 14)
16. Average number of anti-diarrheal agents used per week (Day 28)
17. Abdominal Pain yes or no and scored from 0 to 10 (0-no pain, 10-worst abdominal pain imaginable)
18. Urgency (according to 0-4 VAS scale)
19. Fecal Incontinence (Yes/No)
20. Other comorbid diagnoses
21. Concomitant medications and dosing
22. HRQOL (SF-36) Post-treatment (Attachment 5b)

Data and Safety Monitoring

Adverse Events Reporting – Adverse events are not expected. However, in the event of any unanticipated medical occurrence in a subject directly caused by the drug, it is the responsibility of the Investigator to record all relevant information regarding the medical occurrence on the Sample Collection Study Incident Case Report Form and provide it to the IRB and study sponsors promptly. The Investigator will be responsible for the proper reporting of any potential adverse events (AE) or serious adverse events (SAE) (as defined by general medical standards) to the appropriate authorities. AEs/SAEs related to medication treatment(s) will be reported directly to the manufacturer of the medication product. The investigator will be responsible for ensuring that adequate medical care is provided to a subject for any untoward medical occurrence resulting from this clinical protocol.

Statistics

Since this is a pilot study, simple descriptive statistics will be used to denote outcomes and findings from diagnostic evaluations and treatment. For the diagnostic outcomes, this will include the prevalence of organic gastrointestinal disorders identified as a result of diagnostic testing. For the treatment outcomes, responder and non-responder rates will be described as well as the incidence of adverse effects. Changes in HRQOL will be described in standard fashion.

Ethics

1. IRB approval will be sought from CPHS for initiation of the study. The protocol and related documents will be submitted for review to the UTHealth institutional ethics committee.
2. A written informed consent will be obtained from the participants prior to initiation of the study. Consent will be made available in English.
3. All participants will be provided with the study coordinator's office phone number and fax number for correspondence and answering any queries regarding the study, treatment or any other concerns.

Data handling and record keeping

1. Data will be collected through accessing the individual participant's electronic medical records in the Memorial Hermann Hospital Care4 (inpatient) and UTHealth AllScripts (outpatient) and recorded in the password-protected database electronically.

2. All identifying personal health information will be kept confidential as per HIPAA compliance requirements.
3. Source documents will be accessed only by the principal and co-investigator and will be used solely for the purpose of this study. The records will be accessible for inspection and copying by authorized authorities.
4. All data will be stored electronically in a PIN-protected USB drive and data transfer will be performed through encrypted emails between investigators and staff (if necessary) using institutional email addresses.
5. Patient diaries will be maintained by the patient until the end of study and will be turned in at the end of study to the investigators for abstracting into the study database. Once abstracted, the diaries will be stored with any other had copy study materials in a secured storage container in a locked room maintained by study coordinator personnel.
6. We will share de-identified demographics and results of CSID testing with investigators from the University of Michigan who are performing a similar study aimed and determining the prevalence of CSID.

(Attachment 11)

Quality control and assurance

1. The investigators will meet every month to review the data collected and assess the progress of the project.
2. Study sponsors will be provided with a quarterly report of the progress of the ongoing research including adverse events (if any).

Publication Plan

1. We plan to publish the results of the study in an internationally recognized scientific journal.
2. Napo pharmaceuticals will be provided with the finalized manuscript prior to submission as part of the Grant Agreement.
3. We will make the results of the study available to the participants within 8 weeks of final analyses. It will either be handed to them on their next routine follow up or sent to them by mail, whichever is earlier.

Funding

1. [REDACTED]
2. The remainder of the diagnostic evaluations are considered standard of care and patients will be billed through their insurance in accordance with standard operating procedures for these tests and procedures.

3. Pre-authorization for insurance coverage for these tests will be sought to ensure that you will not be billed later because test was done but insurance later informed you that the test wasn't covered. If specific tests or evaluations are not covered by insurance/Medicare, patients will be given the choice of not undergoing that testing or covering the cost out of pocket.

Conflicts of Interest

The authors disclose no conflicts of interest.

Limitations of the study

1. Participants will not be monitored as inpatients during the study period. This introduces the possibility of confounding factors including variation in diets and excessive use of other rescue medications for symptomatic relief
2. Small sample size of 25 patients for the pilot treatment (crofelemer) arm
3. Short follow up period of 4 weeks to assess effects of the crofelemer will limit any longer-term observations or conclusions regarding chronic therapy with this medication

Based on the results of this pilot study, a randomized control multi-center clinical trial may be warranted with a larger cohort and longer treatment and follow up duration. We are hoping that this study would set up a base for future investigators to explore the potential uses of crofelemer from chronic idiopathic diarrhea given the prevalence of the condition and the absence of FDA approved therapies.

Attachments

1. Curriculum Vitae of the Principal Investigator
2. Written Informed Consent Form to participate in the clinical trial with HIPAA authorization
3. Template of Sample Entry of Daily Symptom Diary
4. Written Informed Consent Form Esophagoduodenoscopy and Colonoscopy
5. SF-36: Health-related Quality of Life Questionnaire Form Pre-Treatment Survey (5a) and Post-Treatment Survey (5b)
6. Crofelemer Package Insert
7. Patient Education Sheet on Crofelemer
8. Patient Education Sheet on Esophagogastroduodenoscopy procedure

9. Patient Education Sheet on Colonoscopy procedure
10. University of Michigan CSID Protocol

Figure 1. A Chemical Structure of crofelemer.

[figure not shown]

Figure 2. Bristol Stool Scale Chart (Reproduced by permission of the late Dr K W Heaton, Reader in Medicine at the University of Bristol. © 2000 Norgine Pharmaceuticals Ltd.) [61]

[figure not shown]

Figure 3. Schematic Design of the Study

[figure not shown]

Table 1. Adverse Reactions Occurring in at Least 2% of Patients in the 125 mg Twice Daily Group

Adverse Reaction	Crofelemer 125 mg BID*N = 229 n(%)	Placebo N = 274 n(%)
Upper respiratory tract infection	13 (5.7)	4 (1.5)
Bronchitis	9 (3.9)	0
Cough	8 (3.5)	3 (1.1)

Flatulence	7 (3.1)	3 (1.1)
Increased bilirubin	7 (3.1)	3 (1.1)
Nausea	6 (2.6)	4 (1.5)
Back pain	6 (2.6)	4 (1.5)
Arthralgia	6 (2.6)	0
Urinary tract infection	5 (2.2)	2 (0.7)
Nasopharyngitis	5 (2.2)	2 (0.7)
Musculoskeletal pain	5 (2.2)	1 (0.4)
Hemorrhoids	5 (2.2)	0
Giardiasis	5 (2.2)	0
Anxiety	5 (2.2)	1 (0.4)
Increased alanine aminotransferase	5 (2.2)	3 (1.1)

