2. Assess the diagnostic yield, in terms of identification of treatable etiologies, of commercially available diagnostic evaluations in adult, non-HIV patients with chronic idiopathic diarrhea; i.e., evaluate which tests, among the standard diagnostic tests commonly conducted as part of the evaluation of chronic idiopathic diarrhea, are most likely to identify a treatable cause of the diarrhea.
3. Assess the usefulness of CSID testing in adults with chronic idiopathic diarrhea via sucrase enzyme level testing on small intestinal biopsies, and ¹³C-SBT.
4. Analyze the relationship between chronic idiopathic diarrhea and health-related quality of life and assess the impact of crofelemer treatment on health-related quality of life

Details of the Study

Definition of Chronic Diarrhea - Persistent increase in bowel movement frequency (≥ 3 bowel movements per day or ≥ 20 bowel movements per week) **AND** decrease in consistency of $>50\%$ stools (liquid or watery-Bristol Stool Form Scale type 6 or 7) for more than 4 weeks [33].

Outcome measures

Primary Response to crofelemer- A 50% decrease in mean stool count per week by the end of week 4

Secondary Responses to crofelemer- An improvement (decrease) in stool consistency by more than 2 levels in the Bristol stool scale (Figure 2) [34,35].

2. Changes in HRQOL at T0 and at T+4 weeks

3. Descriptive analysis of the frequency of identified etiologies of chronic diarrhea and the frequency of abnormal diagnostic test results leading to the identification of those etiologies

Treatment Failure/Non-responder -

1. Failure to meet the primary response definition
2. Medication non-compliance: Subjects who missed more than a total of four doses over the 4-week course.
3. Subjects who fail to record at least 80% of the daily symptom diary.

Inclusion Criteria

Males and females between age 18-75 years with chronic diarrhea (defined as 3 non-bloody loose stools per day or more than 20 non-bloody loose stools per week for more ≥ 4 weeks) and Bristol Stool Form Scale for stool consistency of 6/7 with $>50\%$ stool without an obvious cause after evaluation for organic etiologies. Patients of all ethnicities will be included in the study.

Exclusion Criteria

Since the study focuses on chronic idiopathic diarrhea, subjects who may have other organic pathologies or comorbidities that may explain the cause of diarrhea will be excluded.

1. Hematochezia (potentially related to an organic cause).

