Based on estimated prevalence of identifiable causes of chronic diarrhea in approximately 50% of adult patients and an estimated non-eligibility prevalence of up to 75% of prospective patients, to enroll 25 patients who meet the eligibility criteria for the study, we are estimating that approximately 100 patients will be required to undergo evaluation for this pilot study. This will be achieved over a period of 12-18 months starting from Fall 2019.

Since this is a pilot study with limited data available of the effect of the drug on the specified population, a sample size of 25 subjects is considered safe and feasible to inform potential future randomized controlled trials.

Criteria for termination of trial:

1. Severe unanticipated adverse effects of the drug in the participants
2. Inability to enroll stipulated number of participants over the anticipated study time
3. Withdrawal of more than 50% of the selected subjects from the study. Please note that subjects may withdraw voluntarily from the study at any time of the subject duration. He/she will be required to write a written request addressed to the PI, explaining the reason for withdrawal. New subjects will be enrolled to the study after the screening period, if possible during the total study duration.
4. Enrollment of 25 subjects into the treatment phase or 100 patients in the diagnostic phase, whichever occurs first.

Number of visits/encounters

Four clinic visits at EDDC

1. Pre-screening assessment of subjects (4-8 weeks prior to treatment phase)
2. Discussion of the results of diagnostic tests and evaluations; initiation of treatment with crofelemer 125 mg tablets twice daily (BID) (Day 1) (Attachment 7)
3. Mid-study follow-up (Day 14) for symptomatic evaluation of diarrhea and any adverse events
4. Final post-treatment follow-up on Day 29 **OR** the first business day after completion of treatment

PHASE 1: SCREENING PERIOD

A careful, detailed and comprehensive medical, surgical, and social history will be obtained to categorize the diarrhea and rule out obvious organic causes of diarrhea. All of these diagnostic tests are considered standard of care for the evaluation of chronic idiopathic diarrhea.

The order in which these investigations will be performed will be tailored on a case-to-case basis (patient education for each test is added as an attachment and mentioned in parenthesis)–

1. Complete Blood Count (CBC)
2. Comprehensive Metabolic Panel (CMP)

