3. HIV Screening – To screen patients for the study as our study focuses on non-HIV patients only (if not done in previous 6 months)
4. Esophagastroduodenoscopy (Attachment 8) and Colonoscopy (Attachment 9)– (performed by PI) with random and (if required by endoscopic findings) targeted biopsies of the UGI (duodenum) and LGI (colon) tract mucosa sent to the department of pathology for analysis as well testing for CSID (duodenal biopsies)
5. Stool multiplex panel for the following gastrointestinal pathogens:

Campylobacter

Cryptosporidium

E. coli O157

Enterotoxigenic E. coli (ETEC)

Shiga Toxin-producing E. coli (STEC)

Giardia lamblia

Norovirus GI/GII

Rotavirus A

Salmonella

Shigella

Adenovirus 40/41

Entamoeba histolytica

Vibrio cholera

Yersinia enterocolitica

Clostridium difficile

6. Urine Pregnancy Test when clinically indicated
7. Thyroid Panel: Thyroid stimulating hormone and free T4

8. Tissue transglutaminase and IgA
9. C-reactive protein
10. Serum 7C4
11. Gastrin Level
12. Calcitonin Level
13. VIP Level
14. Stool osmolality
15. Stool Qualitative Stool Fat
16. Stool Reducing Substances
17. Stool calprotectin
18. Stool elastase
19. Lactulose Hydrogen Breath Test
20. ¹³C-Sucrose Breath Test
21. HRQOL (SF-36) baseline - This is a questionnaire that consists of 36 questions and asks subjects' views about their health. Subjects will fill this form two times during the total duration of study – at the initial visit prior to starting treatment and once at the end at the post-treatment follow-up (Attachment 5a and 5b).

We estimate that it may take from 4 weeks up to 8 weeks to obtain and complete all the above-mentioned tests.

Patients will be updated by a call from the study coordinator to discuss the results and scheduled the pre-treatment clinic visit.

Diagnostic tests will be denoted as normal, abnormal, or unable to be performed (in the event of insufficient sample, non-compliance, or lab error). Descriptive statistics will be used to denote the percentage of patients with any abnormal diagnostic tests and the frequency of abnormal results for each test, relative to other diagnostic tests, will be computed and recorded for the cohort.

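### The only post-baseline SF-36 is tied to the post-treatment visit, and no treatment outcome has a stated denominator, so patients who stop early can drop out of the results

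*Combined protocol and SAP*

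**What the plan says.** All references are to the combined protocol and SAP.

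- **HRQOL.** Outcome measures lists "Changes in HRQOL at T0 and at T+4 weeks". PHASE 1: SCREENING PERIOD, item 21, has the SF-36 filled in twice, before treatment and "once at the end at the post-treatment follow-up". PHASE 3: POST-TREATMENT FOLLOW-UP fixes that visit: "A post-treatment follow-up visit would be scheduled with the PI on Day 29 or the first business day after completion of the crofelemer course". Number of visits/encounters gives the same timing. Statistics adds only that HRQOL changes will be described in the usual way.
- **Consistency.** Outcome measures asks for an improvement of more than two Bristol levels and names no time point. The diary in PHASE 2: TREATMENT PERIOD records consistency for every bowel movement, and PHASE 3 lists average consistency for Days 0, 14 and 28.
- **Non-responder rules.** Item 1 of Treatment Failure/Non-responder is "Failure to meet the primary response definition". Items 2 and 3 (more than four missed doses; less than 80% of the diary) name no particular response. Nor does the rule in PHASE 2 on fewer than 22 entries.
- **Diary.** It is checked on Day 14 and Day 29 (PHASE 2) and handed in when the study ends (Data handling and record keeping, item 5).
- **Withdrawal.** Criteria for termination of trial, item 3, is "Withdrawal of more than 50% of the selected subjects from the study". The same item provides for new subjects to be enrolled where possible. Statistics says that responder and non-responder rates will be described and gives no denominator.

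**The concern.** A change score needs both forms. If the second form is collected only at a visit tied to the end of the course, and nothing is said about patients who stop before then, the reported change rests on those who stayed. Patients who stop because the drug did not help or was not tolerated are the likeliest to be missing. The trial has one arm, so no comparator would show whether a before-after gain reflects the drug or the selection.

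The impact of treatment on HRQOL is half of secondary objective 4, and the pilot is meant to inform later randomized trials. A similar gap affects the response rates. Without a stated denominator, a rate may be reported over completers, over the 25 planned, or over everyone who started, and these can differ.

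**Working it through.** **1. The plan's own figure.** To treat 25 with "estimated non-eligibility prevalence of up to 75% of prospective patients", the number to evaluate is 25 / (1 − 0.75) = 100. This reproduces "approximately 100 patients will be required to undergo evaluation for this pilot study". The calculation covers ineligibility only. It makes no allowance for withdrawal after treatment starts, and the document gives no expected withdrawal rate.

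**2. The withdrawal limit.** If the selected subjects are read as the 25 treated, 12/25 = 48% does not exceed 50% and 13/25 = 52% does. The trial could therefore continue with 12 withdrawn. This is a termination limit, not a forecast.

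**3. HRQOL.** Item 21 of PHASE 1 allows two SF-36 forms, and PHASE 3 places the second at the final visit. No SF-36 is planned at Day 14, at stopping or at exit. Statistics has no rule for a missing second form. The default analysis set is therefore the patients with both forms, that is, those who reach the final visit.

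**4. What the missed-dose rule catches.** At two tablets a day for 28 days, a patient whose last full dosing day is k misses 2 × (28 − k) doses. This exceeds 4 when k is 25 or less: k = 25 gives 6, k = 26 gives 4. Anyone who stops by Day 25 is a non-responder, provided that the patient stays in the denominator. The same patient may have no second SF-36.

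**5. Consistency.** The definition has no time point. Day 14 and daily values exist, as does a Day 28 value for those still keeping the diary. Item 1 of the non-responder list covers the primary response only; items 2 and 3 and the 22-entry rule could be read to cover consistency or not. Scoring early stoppers as failures and leaving them out are both compatible with the text.

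**6. Replacement.** Suppose 5 of 25 withdraw and all 5 are replaced: 30 have started and 25 finish. A 40% rate among the 25 finishers is 10 responders; over all who started it is 10/30 = 33%. The plan does not say which would be reported, and this applies to the primary response as well.

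**7. Illustration of size (all inputs assumed).** Let w be the share of 25 who stop early and have no final data. Completers gain 10 points on one SF-36 scale, and 40% of them respond on consistency.

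- All-treated change, stoppers gaining 0: 10 × (1 − w).
- All-treated change, stoppers losing 5: 10 × (1 − w) − 5w.
- Consistency rate, stoppers as non-responders: 0.40 × (1 − w).

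| Stopping early | w | Completers' change | All treated, stoppers 0 | All treated, stoppers −5 | Consistency: completers | Consistency: all treated |
|---|---|---|---|---|---|---|
| 3 of 25 | 0.12 | 10 | 8.8 | 8.2 | 40% | 35% |
| 5 of 25 | 0.20 | 10 | 8.0 | 7.0 | 40% | 32% |

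If stoppers change as much as completers, the all-treated SF-36 change stays at 10 and there is no bias.

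**The case against.** A reader might infer three stronger claims, and the objections to them are sound.

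- **That only the primary response has a rule for early stoppers, so the consistency rate must be completers-only.** The non-responder list follows all the outcome measures, consistency is itself called a response, and the dose and diary items are not limited to the primary. They can fairly be read to cover consistency. The definition does not depend on Day 28 data either. What stands is that time point, denominator and reach of the rules are unstated.
- **That early stoppers cannot supply the data.** Stopping the drug is not leaving the study, and nothing says that it cancels the Day 29 visit. The consent form is not among the pages available, so any withdrawal terms in it cannot be seen. What stands is that the protocol text does not require the data from these patients.
- **That the same patients are certain to count as failures in the primary rate.** With replacement and no denominator, they may disappear from that rate too.

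It can also be said that this is an uncontrolled, descriptive pilot for which "a sample size of 25 subjects is considered safe and feasible", that no test or decision rests on HRQOL or consistency, and that the size rests on chosen inputs. All of that is true. It limits the weight of the point, but descriptive results still need a defined set of patients.

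**Conclusion.** The point is firm for HRQOL: as written, the plan secures a change score only for patients who reach the post-treatment visit. For consistency, and to a lesser degree the primary response, a completers-only rate is left open rather than prescribed.

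The direction is conditional. The HRQOL change is too favourable if early stoppers do worse than completers; the documents do not say why patients would stop, so bias in the drug's favour is plausible and not established. In the assumed cases, a completers' gain of 10 points overstates the all-treated change by 1.2 to 2.0 points with 3 to 5 of 25 stopping and gaining nothing, and a 40% consistency rate overstates by about 5 to 8 percentage points. The plan names eight SF-36 scales and no single endpoint, so the 10 points stand for any one scale. The correction is worth making because it changes what is collected as well as what is reported.

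**What to change.** - **Number of visits/encounters and PHASE 3.** State that a patient who stops crofelemer is still asked for the post-treatment SF-36 (Attachment 5b) and the diary at four weeks, by mail or telephone if needed, or at exit if leaving the study.
- **Outcome measures and Statistics.** Make all patients who start crofelemer the denominator for both response rates, and keep subjects who are later replaced in it.
- **Consistency response.** Set the end of week 4 as the time point, as for the primary. State that the missed-dose and diary rules apply to it, and that a missing week-4 consistency value counts as non-response.
- **HRQOL reporting.** Report the change by scale with the number of treated patients who have both forms, and add one simple sensitivity value for those without, such as zero change.

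The cost is a wording change and one self-administered form for a few patients, some of whom will decline. The secondary results may look less favourable.
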